Official Title: Foot progression angle modification: an exploratory six-week intervention in people with knee osteoarthritis.

NCT Number: TBD

Document Date: Mar 24th, 2020

Statistical Analysis Plan

Statistical analyses will be performed by an independent statistician. Means and standard deviations will be calculated for each outcome measure and baseline demographic characteristic. Baseline demographic data (e.g. age, body mass index, disease severity) will be examined for between-group differences using unpaired two-tailed t-tests. For all statistical analyses, alpha will be set to 0.05. Any multiple pairwise comparisons will be adjusted using the Bonferroni correction method.

Data will be assessed for sphericity, homoscedasticity, and normality using Mauchley's test, residual versus predicted plots, and quantile-quantile plots. Homoscedasticity and normality assumptions will be confirmed using Levene's test and Shapiro-Wilk's test, respectively. Sphericity assumption violations will be corrected for using the Greenhouse Geisser approach. Violations of homoscedasticity will be corrected for by bootstrapped model parameters. If normality is not met, a non-parametric test will be used.

Primary Hypotheses:

Repeated measures analyses of variance (ANOVA) will be performed to examine the within-group changes in learning outcomes over the six-week intervention. Between-group differences will be examined using a two-way mixed ANOVA, with the repeated measure being the learning outcome (foot progression angle change from baseline during in-lab and at-home walking) and the between-subject factor being group assignment (SMOD vs AMAC).

Secondary Hypotheses:

Biomechanical (knee joint moments), clinical (NRS knee pain, KOOS pain, symptoms, and physical function scores), and difficulty (difficulty of performing the FPA modification) change scores will be examined using an analysis of covariance (ANCOVA) with significant between-group baseline demographic group differences and baseline outcome values included as covariates.

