Official Title: Foot progression angle modification: an exploratory six-week intervention in people with knee osteoarthritis.

NCT Number: TBD

Document Date: March 24th, 2020

Study Protocol

Study Design

This parallel-group randomized clinical trial will consist of a 6-week gait modification intervention, delivered to two groups of older adults with medial compartment knee osteoarthritis (OA). The first group will receive a conventional delivery of gait modification (group name: SMOD), whereby they will practice the gait modification with a specific target (rotate foot 15° inward or outward relative to baseline). The second group will self-select the amount of modification they perform (group name: AMAC), guided by the instruction to “change foot rotation as much as is comfortable”. Foot rotation (toe-in or toe-out walking) is measured during the stance phase of walking as the angle of the foot’s long axis (heel to toe) relative to the direction of walking, and termed foot progression angle (FPA). In-lab and real-world gait analysis will be used to examine how the modification is learned, as well as the effect of the modification on biomechanical and clinical outcomes relevant to knee OA. In-lab assessment will be performed at baseline and a 7 week follow-up, while real-world assessment will be performed during the intervening weeks using wearable sensor technology (a custom sensorized shoe design). Both within-group and between-group comparisons will be made to identify differences in learning, difficulty, biomechanical, and clinical outcomes.

Primary Hypotheses

- H1: Participants receiving the specific FPA target will exhibit improved learning outcomes (e.g. lower error in performance, higher proportion of steps with $\geq 7^\circ$ of change from baseline FPA and lower variability) from week 1 to week 6, as measured during gait modification practice sessions, learning assessments, and during daily walking activity.
- H2: Participants receiving the self-directed FPA modification will exhibit improved learning outcomes (higher proportion of steps with $\geq 7^\circ$ of change from baseline FPA and lower variability) from week 1 to week 6, as measured during gait modification practice sessions, learning assessments, and during daily walking activity.
- H3: We expect FPA variability will be larger in the self-directed group, but both groups will exhibit a similar proportion of steps with $> 7^\circ$ of change from baseline FPA.

Secondary Hypotheses

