directly in front of the treadmill. The SMOD group will be guided to increase their FPA by 15° in either the toe-in or toe-out direction (determined by the gait screen). A line of tape will be aligned on the mirror according to the target FPA, as we have done previously [5, 17]. This mirror-based method of providing a target for the FPA modification was shown to be similarly effective when compared to feedback delivered using an expensive real-time motion capture system, but with significantly greater clinical feasibility. The AMAC group will be instructed to increase their FPA by “as much as is comfortable”. The mirror will be provided during practice sessions; however, no tapeline will be placed. The amount of time spent with the feedback (mirror) visible will be progressively reduced (faded feedback) across the six weekly practice sessions in order to reduce the reliance on feedback [18]. Before and immediately after the practice sessions, the participant will perform a warm-up and cool-down walk while wearing the sensorized shoes (10-minute outdoor standardized walking loop). This will provide a repeatable non-laboratory-based measure of FPA. Both groups will be encouraged to practice their gait modification at any opportunity during their daily at-home walking. Practice sessions will be led by a kinesiologist with experience delivering gait modification interventions.

Learning will be measured during 1) practice, 2) immediate and delayed retention tests, 3) dual-task tests, 4) transfer tests, and 5) during at-home/community walking. Each test (2-4) will last 1 min and be collected at each practice session. For the SMOD group, the absolute performance error (absolute error = |performed FPA – target FPA|), FPA variability, and the proportion of steps with >7° of change from baseline FPA will be measured using the sensorized shoe. For the AMAC group, FPA variability and the proportion of steps with >7° of change from baseline FPA will be measured. Retention tests will occur immediately before (starting at practice session 2) and after practice bouts. The participant will be asked to perform their gait modification as accurately as possible for 1 minute. Dual-task testing will be performed identically to the baseline assessment described above; however, the participant will be asked to simultaneously perform their gait modification. Lastly, transfer testing will be performed during stair ascent and descent in the same manner as the baseline assessment.

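### The SAP names no deciding test for H1 or H2 and omits the Protocol's single primary outcome, while testing every learning outcome at 0.05 and adjusting only pairwise comparisons

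*SAP*

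**What the plan says.** The opening paragraph of the SAP fixes the error rate and gives the only multiplicity rule: "For all statistical analyses, alpha will be set to 0.05. Any multiple pairwise comparisons will be adjusted using the Bonferroni correction method". No adjustment, ordering or decision rule is given across outcomes, settings or hypotheses.

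The Protocol, under Primary Hypotheses, words H1 as follows: "Participants receiving the specific FPA target will exhibit improved learning outcomes (e.g. lower error in performance, higher proportion of steps with" at least 7 degrees of change, and lower variability. That makes three outcomes, given as examples, so the list is open. H2 reads: "Participants receiving the self-directed FPA modification will exhibit improved learning outcomes (higher proportion of steps with" at least 7 degrees of change, and lower variability, so two outcomes. Both hypotheses apply "as measured during gait modification practice sessions, learning assessments, and during daily walking activity". The Gait modification intervention section splits these settings further: "Learning will be measured during 1) practice, 2) immediate and delayed retention tests, 3) dual-task tests, 4) transfer tests, and 5) during at-home/community walking".

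Under Participants, the Protocol names one primary outcome: the change in absolute FPA performance error. It is measured at immediate and delayed retention, week one against follow-up, and is defined only for SMOD because AMAC has no target. The SAP mentions neither performance error nor retention. For the primary hypotheses it plans repeated measures ANOVAs on learning outcomes, without listing which ones. For the group comparison it plans a mixed ANOVA on FPA change from baseline, in the lab and at home.

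**The concern.** H1 and H2 are stated as primary and directional, yet a reader of the SAP cannot tell which result would confirm or refute either. The Protocol has a primary outcome that could settle H1, but the analysis plan does not use it. H2 has no counterpart, because performance error cannot be calculated in AMAC.

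The 0.05 level therefore attaches to each ANOVA and not to the conclusion that H1 or H2 is supported. After the data are in, support could be claimed from whichever outcome and setting happened to be significant, and nothing in the plan would rule that out.

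**Working it through.** Neither document states an error rate across tests, so there is no planned figure to reproduce. The calculation below shows what the open wording allows.

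**Inputs from the documents**
- Level per test: 0.05 (SAP, opening paragraph).
- Outcomes: 3 for H1 and 2 for H2 (Protocol, Primary Hypotheses).
- Settings: 3 in the wording of H1 and H2; 5 numbered items in Gait modification intervention; 6 if immediate and delayed retention are counted separately.
- Participants: 18 per group (Protocol, Participants).

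**Assumptions, not in the documents**
- Each outcome in each setting is a separate test, and any one significant result counts as support.
- There is no true change in any outcome or setting.
- Correlation between tests lies anywhere from 0 to 0.9.

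**Number of tests**
- H1: 3 × 3 = 9, 3 × 5 = 15, or 3 × 6 = 18.
- H2: 2 × 3 = 6, or 2 × 6 = 12.

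**If independent**, the chance of at least one false positive is 1 − 0.95^k:
- H1: k = 9 gives 37.0%; k = 15 gives 53.7%; k = 18 gives 60.3%.
- H2: k = 6 gives 26.5%; k = 12 gives 46.0%.

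**If correlated**, simulation of k equally correlated two-sided z tests (200,000 draws) gives:

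| Correlation | H1, 9 tests | H1, 15 tests | H1, 18 tests | H2, 12 tests |
|---|---|---|---|---|
| 0 | 37.1% | 53.8% | 60.4% | 46.1% |
| 0.3 | 32.6% | 45.7% | 51.0% | 39.8% |
| 0.5 | 27.0% | 36.2% | 39.8% | 31.7% |
| 0.7 | 20.2% | 25.7% | 27.7% | 23.2% |
| 0.8 | 16.6% | 20.3% | 21.7% | 18.6% |
| 0.9 | 12.4% | 14.5% | 15.1% | 13.5% |

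The planned tests are ANOVAs, so the same question was simulated with one-way repeated measures ANOVAs in 18 people over six weeks, with the correlation placed on the weekly errors. For 18 tests the result is about 60% at correlation 0, 56% at 0.3, 47% at 0.5, 36% at 0.7 and 26% at 0.8. For 9 tests it is 37%, 35%, 32%, 24% and 20%.

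**Counting only false positives in the predicted direction**, 18 tests give 1 − 0.975^18 = 36.6% if independent and 20.0% at correlation 0.5.

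**If H1 is judged on the named primary outcome alone**
- One test at 0.05: 5%.
- Immediate and delayed retention tested separately at 0.05: 1 − 0.95² = 9.75% if independent.
- The same two tests at 0.025 each: 1 − 0.975² = 4.9%.

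**The case against.** The strongest reply is that the large figures depend on a rule the documents never state. H1 and H2 join their outcomes and settings with *and*. If all had to be significant, the error rate would be at most 5%. The separate tests are also a construction, since the SAP does not list its ANOVAs. The sample-size paragraph puts both retention tests at both times into one model, where they are levels of a factor and contrasts among them would fall under the Bonferroni rule. The outcomes come from one FPA signal in the same people, so high correlation is plausible. The named primary outcome matches the first outcome listed in H1. The title calls the study exploratory.

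Most of this stands as a limit on the size. A reader might infer that H1 carries roughly a 40% to 60% chance of a false positive. That needs all 18 tests, the any-one-counts rule and a correlation between z tests of no more than about 0.5, and the documents supply none of the three.

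A reader might also extend the count to H3, for 18 + 12 + 12 = 42 tests. The text does not support that. H3 says "We expect FPA variability will be larger in the self-directed group, but both groups will exhibit a similar proportion of steps with" more than 7 degrees of change. It names no settings, and its second half predicts similarity, so a false-positive difference there would count against it. The SAP's group comparison is a mixed ANOVA on a different variable.

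The reply does not supply the missing rule. The exploratory label lowers the stakes, but the Protocol still has primary hypotheses, a named primary outcome and a sample size calculated for 80% power at 0.05. Nor does the overlap between the named outcome and H1 help while the SAP is silent on it, and it cannot help H2.

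**Conclusion.** The concern holds in a limited form. The SAP does not carry over the Protocol's primary outcome and gives no rule for deciding H1 or H2 from several outcomes and settings, each tested at 0.05. That much is plain from the text and needs no assumption.

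The size is conditional. If any one significant result were taken as support and nothing truly changed, the false-positive chance for H1 would be about 15% to 60% with 18 tests, the low end at correlation 0.9 and the high end at independence. With H1's own three settings it would be at most about 37%. These ranges describe what the wording permits; they are not the plan's error rate. For an exploratory trial this is an inexpensive improvement worth making, and it does not undermine the design.

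**What to change.** Amend the SAP as follows.

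- **H1:** make the Protocol's primary outcome the one deciding test, namely the change in absolute FPA error from week 1 to follow-up in SMOD. Put immediate and delayed retention in one repeated measures model and take the single test of change over time. Alternatively, test each at 0.025.
- **H2:** name one deciding outcome and setting from data already planned, for example the proportion of steps with at least 7 degrees of change at delayed retention in AMAC.
- **Time points and threshold:** state which visits supply the first and last values. H1 and H2 run from week 1 to week 6, the sample-size paragraph uses follow-up, and the retention test before practice starts only at session 2. Use one form of the 7-degree threshold, which appears both as at least 7 and as more than 7.
- **Everything else:** report the remaining outcome-by-setting results as exploratory estimates with 95% confidence intervals, with no claim of support from p-values.

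This costs SAP wording only, with no new data or participants. The downside is that other outcomes and settings, including home walking, can no longer carry a primary claim alone. Bonferroni over all 18 H1 tests (0.05/18 = 0.0028 each) would also hold the error rate, at 4.9% if independent, but it sets a strict threshold for 18 people per group.

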A total of 36 individuals will be recruited for this study, 18 in each group. Approximately 60% in each group will be female. The primary outcome measure of this study is the change in absolute FPA performance error (the difference between the performed and the targeted FPA), which is indicative of how ‘accurate’ the patient is when performing the modification. This outcome measure is only relevant to the SMOD group, who have a specific target for their modification; therefore, allowing an error value to be calculated. This outcome will be measured during immediate and delayed retention at week one compared to follow-up and will provide evidence of the extent to which motor learning has occurred. Previous FPA performance error during immediate retention testing after a six-week FPA modification resulted in a small effect (Cohens $d = 0.35$) [3]. We are also interested in exploring the clinical and biomechanical differences between the SMOD and AMAC gait modification groups; however, no study has previously compared these methods of gait modification. Therefore, we will be conservative and base our sample size calculation on the between-within interaction effect of a 2×4 (group = 2: SMOD vs AMAC; measure = 4: immediate and delayed retention tests at week 1 and follow up) repeated measures ANOVA with an effect size of $f = 0.175$ ($f = d / 2$). With power = 0.8 and alpha = 0.05, a total sample of 30 is required [4]. With a conservatively estimated attrition of 15%, we will recruit 36 participants total (18 per group).

Procedures

Recruitment and screening

Volunteers will be recruited via print and social media, and via our database of previous participants who have indicated interest in participating in future studies. Interested volunteers will be screened via phone, email, or our lab website by the study coordinator to assess inclusion and exclusion criteria. Those deemed preliminarily eligible will be invited to attend a gait screening appointment. Eligible participants who pass the gait screen will be referred for a radiographic assessment of their knees to confirm the presence of structural signs of knee OA.

Standing, semi-flexed posteroanterior radiographs of both knees will be taken. A trained assessor will grade all radiographs based on the KL criteria. Those passing all screening requirements will be invited to enroll in the study.

Gait screening

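### The SAP's bootstrap remedy for unequal variances is unspecified, and an ordinary bootstrap with about 15 completers per arm would not hold the stated 5% error rate

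*SAP*

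**What the plan says.** The opening paragraph of the SAP fixes the error rate: "For all statistical analyses, alpha will be set to 0.05". The next paragraph sets the assumption checks. Residual plots are inspected, and then "Homoscedasticity and normality assumptions will be confirmed using Levene's test and Shapiro-Wilk's test, respectively". If variances differ, the instruction is: "Violations of homoscedasticity will be corrected for by bootstrapped model parameters". The SAP does not state the interval or test built from the bootstrap, the resampling unit or the number of resamples.

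The between-group analyses that this can affect are the two-way mixed ANOVA of FPA change (SAP, Primary Hypotheses) and the ANCOVAs of change scores in knee moments, pain, KOOS and difficulty (SAP, Secondary Hypotheses).

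On sample size, the protocol's Participants section says: "With a conservatively estimated attrition of 15%, we will recruit 36 participants total (18 per group".

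The arms differ in how the amount of modification is set. SMOD participants are "guided to increase their FPA by 15° in either the toe-in or toe-out direction" (Gait modification intervention). For AMAC, "The second group will self-select the amount of modification they perform (group name: AMAC" (Study Design).

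**The concern.** A correction for unequal variances should bring the test back to its stated error rate. In small samples the common bootstrap intervals do not. The resampled spread of a mean understates its standard error, and the interval makes no allowance for estimating the variance from few participants. Both faults make intervals too narrow. A residual bootstrap that pools residuals across arms does not address unequal variances at all.

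The step could well be triggered for FPA change. One arm aims at a common 15° and the other chooses its own amount, so a wider spread between people in AMAC is plausible, though no figure supports it. If the step is triggered and an ordinary bootstrap is used, the between-group tests would be reported at 0.05 while running above it.

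**Working it through.** **Inputs.** From the documents: alpha 0.05; 30 participants required, 15% attrition, 36 recruited, 18 per arm; Levene's test as the trigger. Assumed: normal data, two-sided tests, and a ratio of arm SDs from 1 to 3.

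**Plan's own figure.** 30 / (1 − 0.15) = 35.3, rounded up to 36, which matches. Conversely 36 × 0.85 = 30.6, so about 15 completers per arm.

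**Approximation by hand, 15 per arm.** The bootstrap standard error of an arm mean is smaller than the usual one by √(14/15) = 0.966. A percentile interval on normal data therefore rejects when the usual statistic exceeds about 1.96 × 0.966 = 1.893, whereas t on 28 df needs 2.048. The statistic has approximately a t distribution with df = (1 + r²)² × 14 / (1 + r⁴), where r is the SD ratio:

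- r = 1: df = 4 × 14 / 2 = 28; P(|t| > 1.893) = 6.9%
- r = 2: df = 25 × 14 / 17 = 20.6; 7.2%
- r = 3: df = 100 × 14 / 82 = 17.1; 7.5%

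**Simulation, two-group contrast, 15 per arm, method always applied.** Type I error in %, as ranges over runs of 6,000 to 20,000 trials with about 1,000 resamples each:

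| Method | r = 1 | r = 2 | r = 3 |
|---|---|---|---|
| Percentile | 6.7 | 7.1-7.6 | 7.3-7.8 |
| BCa | 6.7 | 7.4-7.8 | 7.8-8.0 |
| Basic | 6.7 | 7.2 | 7.4 |
| Uncorrected pooled test | 4.8 | 5.1-5.7 | 5.2-5.7 |

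Over the same range Welch gives 4.8-5.3, a studentised bootstrap-t 4.5-5.4 and a wild bootstrap-t 4.8-5.1.

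**ANCOVA with one baseline covariate, 15 per arm, r = 2.** Case-resampled bootstrap 7.2-7.7%, percentile resampling within arm 7.9%, residual bootstrap 8.3%, uncorrected 5.8%. HC3 gives 4.3-4.6%, bootstrap-t 5.1% and wild bootstrap-t 5.5%.

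**Allowing for the trigger.** Levene's test rejects in about 58-62% of trials at r = 2. Among trials where it rejects, the percentile bootstrap runs at about 6.4-6.9%. The full rule (ordinary bootstrap if Levene rejects, otherwise the standard test) gives 5.2% at r = 1, 5.9% at 1.5, 6.8% at 2 and 7.2% at 3.

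**Repeated-measures layout.** Two groups by four measures, 15 per arm, correlation 0.7 assumed, 6,000 trials. For the group effect and one group-by-time contrast, the full rule gives 7.0-7.4% at r = 2 and 7.7-8.2% at r = 3. Welch gives 5.3-6.0%; the contrast ran slightly high for every method. The overall interaction test was not simulated.

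**Unequal completers, 17 versus 13, r = 2 to 3.** With the larger SD in the smaller arm: pooled 7.2-7.9%, percentile 7.6-8.1%. With the larger SD in the larger arm: pooled 3.1-3.6%, percentile 7.2-7.4%. Welch stays at 4.4-5.2%.

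Monte Carlo standard error is about 0.2-0.3 percentage points.

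**The case against.** The strongest reply is that the SAP names no bootstrap. A reader might infer that its remedy is anti-conservative in itself, so that the planned alpha becomes 7-8%. The documents do not support that. A studentised or wild bootstrap-t fits the same sentence and holds about 5%. What stands on the other side is that every ordinary interval checked is too liberal, so a method that works has to be named.

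Second, 7-8% is the rate if the bootstrap is always applied. The SAP applies it only on a detected violation, which lowers the rate to the figures for the full rule. This stands, and it moderates the size without removing it.

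Third, a reader might conclude that making no correction is better. That holds only for near-equal arms. At 17 versus 13 the uncorrected test is itself well off 5%, in a direction that depends on which arm has the larger spread.

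Fourth, unequal variances are not documented. The third primary hypothesis expects larger FPA variability in the self-directed group, but that is variability as an outcome, not the between-person SD of FPA change. The expected smaller average change in AMAC could even limit spread. For pain, KOOS, moments and difficulty the documents give no reason to expect unequal variances.

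Fifth, the scope is limited. The named primary outcome, absolute FPA error, exists only in SMOD, so no comparison of arm variances arises. Where the hypotheses predict no group difference (the sixth and part of the third), excess rejections would count against them. The trial is also titled exploratory. These points stand and limit the severity.

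**Conclusion.** The concern holds in limited form. The SAP leaves its remedy for unequal variances open, and the ordinary ways of carrying it out miss the stated alpha at this sample size. The excess is nil or negligible when variances are equal, about one percentage point at an SD ratio of 1.5 and about two at ratios of 2 to 3, reaching about three in the repeated-measures layout at ratio 3.

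This rests on normal data, about 15 completers per arm, an assumed SD ratio and an ordinary bootstrap being the one used. It applies to the between-group mixed ANOVA and the secondary ANCOVAs. Severity is minor to moderate, with moderate confidence: the error rates were consistent across methods and runs, but the SD ratio and the intended bootstrap are unknown.

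**What to change.** Replace the SAP sentence on violations of homoscedasticity with:

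> Between-group contrasts will use methods that allow unequal variances: a separate residual variance per arm with Satterthwaite or Kenward-Roger degrees of freedom (or Welch tests on per-participant contrasts) for repeated measures, and HC3 standard errors with a t reference for ANCOVA. Any bootstrap will be studentised and used only as a sensitivity analysis.

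Because this applies whatever Levene's test shows, the two-stage rule disappears for these contrasts. If a bootstrap is kept, the SAP should state its type, that participants are the resampling unit, and the number of resamples.

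The cost is one sentence and standard software, with no change to conduct or sample size. The downside is a slight loss of precision if variances turn out equal. The Welch and HC3 options were checked by simulation; the mixed model with Satterthwaite or Kenward-Roger degrees of freedom was not.

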Stair ascent and descent will be performed while wearing the sensorized shoes. This will take place at a building nearby the laboratory (5-minute walk) because of the availability of continuous linear sets of stairs for multiple flights. This allows the use of the sensorized shoe for measuring FPA during stair ascent and descent. These FPA data will be compared with transfer test data (details included below) examined at several points throughout the intervention. These same shoes will be provided to the participant to measure real-world FPA during at-home and community walking.

Sensorized shoes

A custom inertial sensor consisting of a 3-axis accelerometer (signal range: $\pm 4g$), gyroscope ($\pm 500^\circ/s$), and magnetometer ($\pm 1200\mu T$), sampling data at 100 Hz will be embedded in the sole of the shoe. A previously published custom sensor fusion algorithm [13], programmed into a microcontroller, calculates the FPA in real time and stores it on a microSD card for later extraction. The sensorized shoe design and algorithm has been validated during treadmill [14] and over-ground walking [15] with excellent validity and reliability (absolute error = 1.7° and intraclass correlation coefficients > 0.9).

Randomization

Once deemed eligible and baseline data collection is complete, each participant will be randomized to either the SMOD or AMAC group. Randomization will be performed using an *a priori* block-stratified approach based on sex and KL grade. A predetermined randomization matrix will be computed [16] by a team member not involved in testing or the intervention. Group allocations will be stored in opaque envelopes, which will be opened in a sequential manner after baseline testing and before the first practice session. The group allocation will be communicated to the study trainer via email.

Gait modification intervention

Both groups will attend six practice sessions conducted weekly, which will last approximately 1 hour each. Walking practice will be conducted on a treadmill with a full-length mirror placed

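### The SAP names no start-to-end contrast for within-group learning and does not exempt the hypothesised comparison from Bonferroni, so its threshold is left open between 0.05 and about 0.003

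*SAP*

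**What the plan says.** **Protocol, Participants (primary outcome).** "The primary outcome measure of this study is the change in absolute FPA performance error". It exists in one arm: "This outcome measure is only relevant to the SMOD group, who have a specific target for their modification". On timing: "This outcome will be measured during immediate and delayed retention at week one compared to follow-up".

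**Protocol, Primary Hypotheses.** H1 (SMOD) and H2 (AMAC) predict improved learning outcomes "from week 1 to week 6, as measured during gait modification practice sessions, learning assessments, and during daily walking activity".

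**Protocol, Gait modification intervention.** "Both groups will attend six practice sessions conducted weekly". Retention tests belong to these sessions. The one given before practice starts only at session 2.

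**Protocol, sample-size paragraph.** The calculation uses a 2×4 layout, the four measures being the two retention tests at week 1 and at follow-up. It takes d = 0.35, converted to f = 0.175, and arrives at 30 in total, raised to 36 (18 per group) for 15% attrition.

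**SAP, Primary Hypotheses.** "Repeated measures analyses of variance (ANOVA) will be performed to examine the within-group changes in learning outcomes over the six-week intervention". The opening paragraph adds "For all statistical analyses, alpha will be set to 0.05" and "Any multiple pairwise comparisons will be adjusted using the Bonferroni correction method".

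The SAP does not give the number of time levels, a start-to-end contrast, or the set of pairwise comparisons that the Bonferroni rule covers.

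**The concern.** The hypotheses and the primary outcome are about the end compared with the start. The repeated measures F test asks something wider: whether any time point differs from any other, in any direction. A transient bump or dip in mid-programme can make it significant, so a significant F does not by itself support H1 or H2. A further comparison of end with start is needed, and the SAP's only rule for such comparisons is Bonferroni.

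Two things are at stake. The hypothesised comparison may be held to a much stricter level than 0.05, to pay for comparisons that nobody hypothesised. And because neither the time levels nor the family is fixed, the threshold could be settled after the data are seen.

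**Working it through.** **Inputs.** From the documents: alpha 0.05; d = 0.35; 30 evaluable participants, so 30/2 = 15 in SMOD; six sessions; four measures in the sample-size layout. Assumed, because the documents do not give it: a within-person correlation ρ of 0.5 to 0.7.

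**The plan's own figure.** For the 2×4 interaction, λ = f²·N·4/(1−ρ), with 3 and 3(N−2) degrees of freedom. With f = 0.175, N = 30 gives power 0.80 at ρ = 0.68 and 0.83 at ρ = 0.70. At ρ = 0.5, N = 30 gives 0.59 and N = 46 would be needed. So 30 is reproduced only for a correlation that is not stated. The attrition step is right: 30/0.85 = 35.3, hence 36. This calculation concerns the interaction, not the SMOD start-to-end change.

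**Possible thresholds.** With m levels and all pairs tested, each pair is judged at 0.05/[m(m−1)/2].
- Lone planned comparison: 0.05.
- Four measures: 6 pairs, 0.05/6 = 0.0083.
- Six sessions: 15 pairs, 0.05/15 = 0.0033.

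Other level counts are conceivable. Five (pre-practice retention, sessions 2 to 6) gives 10 pairs and 0.005. Seven (six sessions plus follow-up) gives 21 pairs and 0.0024.

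**Power of the start-to-end comparison.** Two-sided paired t test, n = 15, noncentrality dz·√15, with dz = d/√(2(1−ρ)). At ρ = 0.5, dz = 0.35/√1 = 0.35. At ρ = 0.7, dz = 0.35/√0.6 = 0.452.

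| Threshold | ρ = 0.5 | ρ = 0.7 |
|---|---|---|
| 0.05 (one planned contrast) | 24% | 37% |
| 0.025 (two contrasts, first step) | 16% | 26% |
| 0.0083 (one of 6 pairs) | 7.5% | 14% |
| 0.0033 (one of 15 pairs) | 4% | 7.5% |

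If all 18 SMOD participants are evaluable, the 0.05 row becomes 29% to 44%. For 80% power at 0.05 the SMOD arm alone would need 67 (ρ = 0.5) to 41 (ρ = 0.7).

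**Can the omnibus F be significant without start-to-end change?** Take six sessions, n = 15, ρ = 0.7, and a mean shift of 0.7 SD at session 3 only. The sum of squared deviations is 0.7²×5/6 = 0.408, so λ = 15×0.408/0.3 = 20.4 on 5 and 70 degrees of freedom, and power is 94%. In simulation with the SAP's Greenhouse-Geisser correction the F was significant in 91% of trials, although the true change from week 1 to week 6 was zero.

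**The case against.** **The 0.003 level is not in the documents.** A reader might infer that the key comparison will be judged at about 0.003. That needs six time levels and all 15 pairs in one family. The SAP states neither, and the only level count in either document is four. A comparison tested alone is not a multiple comparison and stays at 0.05. This stands: 0.003 is one possible reading, not the plan.

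**The primary outcome is not one contrast.** It covers immediate and delayed retention, and H1 and H2 span several outcomes and settings. This also stands. A planned contrast keeps its 5% error only once one test is named or the two are adjusted together.

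**The ANOVA itself runs at 0.05 and loses less power than the all-pairs route.** In simulations with n = 15, six sessions, ρ = 0.7 and an assumed exponential learning curve, the corrected F had 24% power against 37% for the planned contrast at d = 0.35. At d = 0.70, a value with no source in the documents, it had 87% against 90%. On the four-measure layout with both retention tests shifting by 0.35 SD, the uncorrected F has 30% (ρ = 0.5) to 49% (ρ = 0.7), above a single two-point contrast, because it uses two measurements at each end. So the large loss belongs to the Bonferroni pair, not to the F test. The F test's weakness is that it does not answer the question.

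**A two-sided contrast can also be significant for worsening.** True, but its estimate and interval show the direction of the start-to-end change, which an omnibus F does not.

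**The trial is exploratory and the method conventional.** Fair, and Bonferroni does control error. But the documents still name primary hypotheses, a primary outcome and an alpha.

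**Conclusion.** The point holds as a gap in specification. The hypotheses and primary outcome are start-to-end changes, and the SAP offers only a general test over time plus a Bonferroni rule with no defined family and no exemption for the hypothesised comparison. The threshold is therefore open: 0.05, 0.0083, or about 0.003 on the six-session, all-pairs reading. At d = 0.35 and n = 15, moving from 0.05 to 0.0083 takes power from 24–37% to 7.5–14%, and to 0.0033 takes it to 4–7.5%. These figures rest on the assumed correlation of 0.5 to 0.7.

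A reader might also infer that a non-significant result would be due to the correction alone. The figures do not support that: even the uncorrected contrast is well short of 80% power at the protocol's effect size. The planned contrast helps, and it answers the right question, but it does not cure the sample size.

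**What to change.** In the SAP:

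1. Pre-specify the SMOD week-1-to-follow-up change in absolute FPA error as the planned primary contrast, reported with a 95% CI and not conditional on the omnibus F.
2. Either name one retention test (immediate or delayed) as primary at two-sided 0.05, or test both with Holm across the two (smaller p-value against 0.025, the other against 0.05).
3. State which session supplies the first delayed-retention value, since that test begins at session 2 and so has no session 1 measurement.
4. Reconcile the endpoints: H1 and H2 end at week 6, the primary outcome at follow-up, and the intervention section places retention tests at the practice sessions.
5. For learning outcomes that both arms have (FPA variability, proportion of steps beyond 7°), use the matching group-by-(end minus start) contrast.
6. Keep the session-by-session ANOVA as a description of the learning curve, state its time levels, and replace Bonferroni with Holm for any remaining pairwise comparisons. Holm controls the same error rate and is never less powerful.

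The cost is some SAP wording and the decisions in items 2 to 4, with the same data and software. One drawback is that simultaneous confidence intervals are less simple under Holm than under Bonferroni.
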